Studies of the upper and lower airways of human infants with RSV bronchiolitis are required to definitively understand pathological mechanisms. Studies in infants are difficult to undertake, especially as the child may be clinically unstable and conventional procedures to obtain samples may be too invasive. Infants who require mechanical ventilation for severe RSV bronchiolitis are tracheally intubated, sedated and have indwelling vascular catheters. This allows access to the respiratory tract and enables blood sampling.

In infants naturally infected with RSV, the presence of virus is generally detected in nasopharyngeal aspirate (NPA) samples (5;9). In the UK it is standard clinical practice to perform NPA sampling by direct suction of secretions. However, because this involves the introduction of a suction catheter into the nostril and then to the back of the nose, this procedure may be relatively unpleasant. Sampling by NPA has been found superior to nasal swabs manufactured from natural products (10;11).

Using nasal swabs in young children is rapid and painless and also accurate for RSV diagnosis (12). There is concordance between nasal and nasopharyngeal (NP) swabs for viral testing (13). In a comparison with NPA, nose and throat swabs were more comfortable and have less risk of harm in a clinical setting, but NPA is still recommended in a hospital context (14). Flocked nylon swabs gave higher viral loads than cotton swabs when using qPCRs for detection of human rhinovirus (15).

Viral load may be obtained from these samples by quantitative polymerase chain reaction (qPCR) of infectious samples. This correlates with disease severity in infected infants (4;5). In adults infected experimentally with RSV, the viral load peaks before maximal clinical symptoms (6). It is a major parameter in quantitating the magnitude of infection (7). In assessing the effects of novel therapeutics in experimental infection, the area under the curve (AUC) of viral load is generally the primary end point (8). To determine this, daily samples over the disease course are required. However, there are concerns regarding the accuracy of viral load detection from routine NPA samples as this is dependent of the amount of mucous suctioned at the same time, which varies enormously from patient to patient.

The current methods of sampling described above have a number of limitations:

- Samples are often diluted in saline which can lead to poor sensitivity
- There is a lack of consistency in the location the sample is obtained from which can affect both diagnostic specificity and reproducibility
- Sampling can be uncomfortable and invasive

Proposal for novel absorption sampling methods

In conjunction with a specialist medical device manufacturing company (Hunt Developments (Midhurst, West Sussex) we have produced novel nasosorption and bronchosorption kits that have CE marking. Both nasosorption and bronchosorption methods use synthetic absorptive matrix (SAM) strips: that look and feel like blotting paper, and will be placed onto the mucosal surface. These are comfortable to use and can be used at frequent intervals over extended periods of time. This non-invasive technique is ideal for infants and children, and it is possible to obtain neat mucosal lining fluid (MLF) even from normal healthy noses. The eluates contain cytokines and chemokines at high detectable levels on multiplex immunoassay.

We would like to use these SAMs to take MLF samples from the nasal and bronchial mucosal surfaces to see if these novel techniques can overcome the problems with current sampling methods. We plan to use these absorption techniques to measure RSV viral load. We also aim to look at the immune response in terms of the anti-viral interferon response (IFN- γ , IFN- λ , IFN- α 2a, IP10, ITAC). In therapeutic studies in the future, it may be possible to document levels of drug (pharmacokinetics) in nasal MLF.

Nasosorption (NS) and bronchosorption (BS)

NS involves using a synthetic absorptive matrix (SAM) to absorb mucosal lining fluid (MLF) in a precise manner from the inferior turbinate. At Imperial College we have used NS in children with allergic rhinitis (16), infants with a family history of atopy (17), and in atopic adults after nasal allergen challenge (NAC) (18). SAM has also been used after experimental human rhinovirus challenge in asthma when both NS and BS were performed (19;20). The [name] group at Imperial have recently compared and validated a variety of SAMs (21), and performed a nasosorption study after cat NAC (22).

The swabs are medical devices, have small handles and are enclosed in a sampling tube. These devices are CE-marked, clean and sterile, and produced in a specialist medical device factory.

Bronchosorption (BS) involves a similar method to NS with a similar SAM material. The SAM is attached to a plastic reinforced catheter that can be introduced through an endotracheal tube to access the bronchial mucosa. [name] [name], respiratory consultant at St Mary's Hospital, has successfully carried out over 700 BS sampling procedures in adults with a range of respiratory diseases. The technique has been very well tolerated, and has permitted cytokines and chemokines to be measured in the bronchial mucosal lining fluid (MLF).

Using a similar but smaller device we hope to take samples from infants ventilated due to severe RSV bronchiolitis. Babies ventilated with severe RSV infection, have an endotracheal tube (ETT) in position that requires suction clearance at regular intervals. Hunt Developments have developed a specialised device for introduction down the ETT, that can be used for BS in babies ventilated for severe RSV bronchiolitis.

As an initial step we will perform a pilot study on tolerability in ventilated infants, and have strict inclusion criteria which will allow inclusion of infants who are stable on the ventilator with low-moderate ventilation and oxygen requirements. We intend to compare inflammatory mediator levels in mucus that has been directly suctioned from the ETT, with levels of mediators in samples obtained using SAM by nasosorption and bronchosorption.

Genetics

Mendelian single gene deficiencies in the form of primary immunodeficiencies have demonstrated the important role that host genetics play in infectious disease outcome. More recently, single gene disorders predisposing to a narrow spectrum of infections have been described. Examples include defects in the IL12-IFN γ pathway predisposing to atypical mycobacterial infections, IRAK4-MYD88 defects to invasive pyogenic infections, and TLR3-IFN defects to herpes simplex encephalitis. Sequencing of the patient samples by whole exome/genome sequencing or linkage analysis will be carried out. One part of this study aims to identify genetic aetiologies of severe RSV infections which will provide tools for molecular diagnosis and genetic counselling.

Summary

In summary this study will compare the novel methods of NS and BS with the standard technique of nasopharyngeal aspiration (NPA) and routine ETT suction. We shall assess the samples for diagnosis of RSV, viral load and immune responses in the airways of babies with RSV infection. We shall also assess the genetics of babies included in this study, to see if they may be vulnerable to RSV infection.

AIMS

The study involves obtaining nasal samples from babies with suspected RSV infection in the emergency department (ED), as well as those admitted to the paediatric wards and PICU at St. Mary's Hospital, London. This will help us to understand the epidemiology of and the host response to RSV infection in infants both hospitalised and in the community. In addition, we shall take nasal samples from infants attending hospital for outpatient appointments, routine elective surgery and admitted to PICU for non-respiratory diagnoses as controls.

The specific aims are:

1. To study different sampling methods; comparing the established method of NPA and tracheal suction to nasosorption and bronchosorption. We will assess sample volumes, clinical tolerability and virology results: especially viral load.
2. To assess the safety and validity of using bronchosorption to take bronchial MLF samples.
3. To study severity of disease and correlate this with quantitative RSV PCR.
4. To study the incidence of RSV A and B infection, different subtypes of RSV infection.
5. To measure the nasal and bronchial mucosal immune response: in terms of cytokines and chemokines, especially those relating to interferons.

6. To identify if there is a genetic predisposition to severe RSV infection
7. To understand feasibility of these sampling processes in preparation for an interventional study potentially in winter 2017-8.

ENDPOINTS

To compare SAM and nasopharyngeal aspirate (NPA) as sampling methods for measuring RSV viral load.

PRIMARY ENDPOINT: RSV viral load

Virology: How do SAM and NPA compare for RSV viral load determination?

We shall also assess:

- Sensitivity, specificity, quantitation
- Utility for RSV-A vs RSV-B

SECONDARY ENDPOINTS

1. Immune Response: Establishing the use of nasal and bronchial sampling to measure the host immune response to RSV. These techniques could then be applied to the study of drug pharmacokinetics for new therapeutics in future clinical studies.
2. Epidemiology and virology: This study will assess the number of babies with upper respiratory tract infections (URTI) presenting to St Mary's Hospital ED, the number of babies with confirmed RSV hospitalised on the Paediatrics Ward and also the number admitted to the PICU. The study will assess the relative incidence of RSV A and B and allow us to determine whether RSV subtype is associated with disease severity.
3. Genetics: To establish whether there is a genetic predisposition to severe RSV infection. To carry out genetic analysis by targeted gene sequencing, next generation sequencing or whole genome SNP typing in order to evaluate any genetic deficiencies.
4. Correlation of qPCR with clinical severity

STUDY DESIGN

Type of Study: Pilot study

Duration: To take place in RSV infection season between October and March, starting in October 2015.

Identification of patients: We shall obtain our study groups from patients attending St. Mary's Hospital, London.

Number and types of Subjects:

A total of 5 participant groups (n = 30 in each group)

Details of each group and respiratory sampling procedures are given below:

- *Group 1:* Babies with suspected respiratory tract infection (RTI) in the ED:
 - Nasosorption (NS) in each nostril
 - NPA
- *Group 2:* Babies with diagnosed RSV infection admitted to paediatric wards:
 - NS (2 to 3 times daily, 4-6 hours apart)
 - NPA daily
- *Group 3:* Babies with diagnosed severe RSV infection in PICU requiring mechanical ventilation:
 - NS (2 to 3 times daily, 4-6 hours apart)
 - NPA daily
 - Bronchial aspirate (BA) daily
- *Control Group 1:* Babies without respiratory symptoms, attending routine outpatient appointments or undergoing elective surgical procedures:
 - Nasosorption (NS) only once
- *Control Group 2 :* Babies without RSV infection but requiring mechanical ventilation in PICU:
 - NS (2 to 3 times daily, 4-6 hours apart)
 - NPA daily

Bronchial aspirate (BA) daily

PROCEDURES

Sampling by Absorption:

Nasosorption: SAM strips will be placed inside each of the nostrils for up to 30 seconds. We will place the SAM on the inferior aspect of the inferior turbinate and middle turbinate. There is minimal discomfort in sampling in these areas. This is a well-tolerated, non-invasive procedure without the need for local anaesthetic.

Bronchosorption: Following clearance of excess mucus by suction, we will introduce the SAM device that will be passed down the ETT to collect bronchial MLF. The device will be passed into the ETT in the same way that a routine suction catheter is introduced. The device will be introduced by the consultant paediatric intensivist or lead physiotherapist gently to a maximum distance of 10cm beyond the end of the ETT, or until it impacts in the bronchial tree. It will then be withdrawn by 5cm and the SAM paper will then be extruded. The device will then be kept in this position for 10 seconds to allow for maximal absorption. The SAM will then be retracted into the device and the device will be withdrawn.

NB for the 2016-2017 season we will not be carrying out the bronchosorption procedure as we have concerns regarding the device and this is being revised accordingly.

Bronchial aspirate:

Routine clearance of excess mucus by suction through the endotracheal tube. We will keep this aspirate that is usually discarded.

Nasopharyngeal aspirate:

NPA will be carried out after the Nasal SAM has been performed. NPAs will be collected using a standardized protocol (23-25). The child is supine and a small suction catheter is used to take fluid from the back of the nose directly with no saline flush is a routine method used to suction babies with a blocked nose in clinical practice.

In babies who are admitted to the ward, sampling will have to consider the impact of nasogastric and other tubes in the airway. If both NS and NPA ~~all~~ samples have to be taken from the same nostril there should be a 10 min interval between each sample

Blood sampling:

If the baby is having a blood test as part of their routine hospital care an additional 1mL will be taken and used to measure markers of infection and inflammation, together with genetic analysis (subject to consent). If the baby requires further blood tests for clinical reasons, we may take further 1ml research samples at up to 2 further time points to see changes in the immune response.

A 1ml blood sample will be taken at the first time point for genetic analysis as detailed below.

Blood Genetics Methods

- i. **Sample collection** Blood samples from the baby will be collected and genetic material extracted
- ii. **Sample processing** To carry out genetic analysis from DNA/RNA isolated from infants by targeted gene sequencing, next generation sequencing or whole genome SNP typing in order to evaluate any genetic deficiencies.
- iii. **Data Collection** It will be necessary to collect demographic and clinical data from the families in order to define clearly clinical phenotypes. This will include data on age, sex, ethnic groups and clinical details relating to the phenotype. These clinical data will be provided by collaborating clinicians from participating hospitals.

INCLUSION AND EXCLUSION CRITERIA

Group 1 and Group 2

Inclusion Criteria

- Infants aged 2 weeks-24 months
- Presentation to the Emergency Department with any upper respiratory tract infection (URTI) in the RSV season (Oct-March).
OR
- Documented RSV infection, admitted to the paediatric wards at St Mary's Hospital.

Exclusion Criteria

- Any local or systemic factor that would influence the safety of nasal sampling.
- Bilateral indwelling nasal catheters or local nasal pathology preventing access for nasal sampling.
- Bleeding disorders.
- The baby is taking part in another interventional study.
- The parents or guardians not able to sign the informed consent from due to limited English or comprehension despite the use of independent interpreter services.
- Limited life expectancy of the baby,

Group 3

Inclusion criteria

- Hospitalised Infants admitted to the PICU at St. Mary's Hospital, aged 2 weeks-24 months with documented RSV infection (by rapid test and/or PCR).
- Infants of weight >2kg.
- On a conventional ventilator with an Endotracheal Tube (ETT) of ≥ 2.0 mm diameter

Exclusion criteria

- Any local or systemic factor that would influence the safety of nasal sampling.
- Bilateral nasal catheters or local nasal pathology preventing access for nasal sampling.
- The baby is taking part in another interventional study.
- Prematurity - corrected gestational age <36 weeks, weight <2kg
- Significant hypoxia or instability precluding ventilator disconnection
- Transcutaneous oxygen saturation of <95% on 60% oxygen
- Risk of bleeding
- Pneumothorax
- Infants receiving oral corticosteroid therapy at any time in past month
- Parents or guardians not able to sign informed consent from due to limited English or understanding despite the use of independent interpreter services.
- Limited life expectancy or a decision to limit management.
- NB – in the event of an exclusion to carrying out bronchial aspirate, (i.e: Significant hypoxia or instability precluding ventilator disconnection
- Transcutaneous oxygen saturation of <95% on 60% oxygen
- Risk of bleeding
- Pneumothorax);

As long as there is no contra-indication to carrying out NPA or nasal SAM sampling, then these children can still be included in the study, but will not require bronchial sampling.

Control Group 1

Inclusion criteria

- Babies, aged 2 weeks-24 months, attending routine outpatient appointments or undergoing elective surgical procedures.

Exclusion criteria

- Any respiratory symptoms
- All other exclusion are the same as Groups 1 and 2

Control Group 2

Inclusion criteria

- Infants aged 2 weeks-24 months.
- Infants ventilated on the PICU for any condition
- Confirmed RSV negative by PCR of respiratory tract samples

Exclusion Criteria

- All exclusions are the same as Group 3
- In addition – any concern about raised intracranial pressure

DATA STORAGE

Anonymised data will be stored in Redcap in the Department of Paediatrics at Imperial College London. The database will be password protected and will be web-based. Only those directly involved in the study will be able to access the data. Individuals will only be identified on the database by their unique alphanumeric identifier; data relating to the subjects' names to this identifier will be stored separately. Any data generated may be stored indefinitely and shared with other researchers outside of the participating sites. This will be done through databases such as ENA and EGA. Any data made available on these databases will be strictly confidential.

DATA ANALYSIS

Levels of inflammatory mediators (e.g. cytokines as pg/ml) across the patient groups will be presented as:

- Raw data: linear and log plots as appropriate
- Box-whisker plots: median/quartile/range
- Heat maps to show correlation between levels of mediators

Statistical analysis will be performed to demonstrate significance of levels of individual biomarkers and molecular signatures.

Data and all appropriate documentation will be stored for a minimum of 10 years after the completion of the study, including the follow-up period.

WITHDRAWAL CRITERIA

Any clinically significant side effects during procedures or withdrawal of consent by the parents or guardians of participants.

ADVERSE EVENTS

DEFINITIONS

Adverse Event (AE): any untoward medical occurrence in a patient or clinical study subject.

Serious Adverse Event (SAE): any untoward and unexpected medical occurrence or effect that:

- **Results in death**
- **Is life-threatening** – refers to an event in which the subject was at risk of death at the time of the event; it does not refer to an event which hypothetically might have caused death if it were more severe
- **Requires hospitalisation, or prolongation of existing inpatients' hospitalisation**
- **Results in persistent or significant disability or incapacity**
- **Is a congenital anomaly or birth defect**

Medical judgement should be exercised in deciding whether an AE is serious in other situations. Important AEs that are not immediately life-threatening or do not result in death or hospitalisation but may jeopardise the subject or may require intervention to prevent one of the other outcomes listed in the definition above, should also be considered serious.

REPORTING PROCEDURES

All adverse events should be reported. Depending on the nature of the event the reporting procedures below should be followed. Any questions concerning adverse event reporting should be directed to the Chief Investigator in the first instance.

Non serious AEs

All such events, whether expected or not, should be recorded.

Serious AEs

An SAE form should be completed and faxed to the Chief Investigator within 24 hours. However, relapse and death due to hospitalisations for elective treatment of a pre-existing condition do not need reporting as SAEs.

All SAEs should be reported to the REC where in the opinion of the Chief Investigator, the event was:

- 'related', ie resulted from the administration of any of the research procedures; and
- 'unexpected', ie an event that is not listed in the protocol as an expected occurrence

Reports of related and unexpected SAEs should be submitted within 15 days of the Chief Investigator becoming aware of the event, using the NRES SAE form for non-IMP studies. The Chief Investigator must also notify the Sponsor of all SAEs.

Local investigators should report any SAEs as required by their Local Research Ethics Committee, Sponsor and/or Research & Development Office.

Contact details for reporting SAEs

[contact], attention [name]

Please send SAE forms to:

St, Mary's Hospital,

[name],

[name]

London

[name]

[contact] (Mon to Fri 09.00 - 17.00)

ASSESSMENT AND FOLLOW-UP

When sampling is well tolerated there will not be follow up of patients, and the patients will not generally be informed of the result of analyses.

REGULATORY ISSUES

ETHICS APPROVAL

The Chief Investigator has obtained approval from the West Midlands – The Black Country Research Ethics Committee. The study must be submitted for Site Specific Assessment at each participating NHS Trust. The Chief Investigator will require a copy of the Trust R&D approval letter before accepting participants into the study. The study will be conducted in accordance with the recommendations for physicians involved in research on human subjects adopted by the 18th World Medical Assembly, Helsinki 1964 and later revisions.

CONSENT

Consent to enter the study must be sought from each participant's parents or guardians only after a full explanation has been given, an information leaflet offered and time allowed for consideration. Signed consent should be obtained. The right of the parent or guardian to refuse to participate without giving reasons must be respected. After the participant has entered the study the clinician remains free to give alternative treatment to that specified in the protocol at any stage if he/she feels it is in the participant's best interest, but the reasons for doing so should be recorded. In these cases the participants remain within the study for the purposes of follow-up and data analysis. All parents and guardians are free to withdraw at any time from the protocol treatment without giving reasons and without prejudicing further treatment.

CONFIDENTIALITY

The Chief Investigator will preserve the confidentiality of participants taking part in the study and is registered under the Data Protection Act.

INDEMNITY

Imperial College Healthcare NHS Trust London holds negligent harm and non-negligent harm insurance policies which apply to this study. Imperial College Healthcare NHS Trust holds standard NHS Hospital Indemnity and insurance cover with NHS Litigation Authority for NHS Trusts in England, which apply to this study.

SPONSOR

Imperial College Healthcare NHS Trust will act as the main Sponsor for this study. Delegated responsibilities will be assigned to the NHS trusts taking part in this study.

PARTICIPANT REIMBURSMENT

There will be no reimbursement for participating in this study as samples are taken opportunistically.

FUNDING

This study is funded by Pulmocide.

AUDITS

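### Does the SAM-versus-NPA comparison need a written rule for reference, pairing and nostrils before it can be analysed?

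*Combined protocol and SAP*

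**What the plan says.** ENDPOINTS makes RSV viral load the primary endpoint and asks how SAM and NPA compare in measuring it. Beneath that, as something also to be assessed, it lists "Sensitivity, specificity, quantitation". It names no reference standard, unit of analysis or rule for combining strips. DATA ANALYSIS deals with mediator levels and biomarker signatures and does not mention viral load or agreement between methods.

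Other sections supply part of the structure:

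- **Schedule (STUDY DESIGN).** Group 1 has nasosorption in each nostril and one NPA. Groups 2, 3 and Control Group 2 have "NS (2 to 3 times daily, 4-6 hours apart", with NPA once a day. Control Group 1 has "Nasosorption (NS) only once" and no NPA, so it is outside the paired comparison.
- **Nostrils (PROCEDURES, Nasosorption).** "SAM strips will be placed inside each of the nostrils for up to 30 seconds".
- **Order (PROCEDURES, Nasopharyngeal aspirate).** "NPA will be carried out after the Nasal SAM has been performed". For ward patients, "sampling will have to consider the impact of nasogastric and other tubes in the airway", and if both "samples have to be taken from the same nostril there should be a 10 min interval between each sample".
- **Access (exclusion criteria, Groups 1 and 2).** An infant is excluded for "Bilateral indwelling nasal catheters or local nasal pathology preventing access for nasal sampling"; a tube on one side does not exclude.
- **Comparator.** The Summary and the first aim treat NPA as the customary method against which the strips are judged.
- **Status.** STUDY DESIGN calls this a pilot study, and the last aim is feasibility for a possible later interventional study.

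**The concern.** The comparison of the two methods is the primary question, yet the plan does not say which strip result is set against which NPA. Most infants contribute several strips per NPA, so the analyst has choices to make: one strip or all, either nostril or both, one session or the whole day, the first day or every day.

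Counting an infant as SAM-positive if any strip is positive can only raise the positive rate as strips are added. Requiring all strips to be positive can only lower it. NPA stays at one sample throughout. Taking the highest strip would bias viral load upwards in the same way, and treating daily pairs from one infant as independent would make confidence intervals too narrow. The reference is also unnamed: Groups 2, 3 and Control Group 2 enter with a known RSV status, which could compete with NPA.

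If these choices were made after the data were seen, an apparent difference between the methods could reflect how many strips were counted and not how well a strip samples virus.

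**Working it through.** **Strips per NPA, from the documents.** Strips = sessions per NPA × nostrils sampled.

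- Group 1: 1 × 2 = 2 (1 with one usable nostril).
- Groups 2, 3 and Control Group 2: 2 × 2 = 4 to 3 × 2 = 6 (2 to 3 with one usable nostril).
- Infants with both methods: 4 × 30 = 120. Those with repeated sessions per NPA: 3 × 30 = 90. Of these, the 30 in Control Group 2 enter as PCR-negative, so detection and viral-load effects concern 60; only false positives concern the other 30.

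These are strips collected. The documents do not say that each is assayed separately for virus. Strips also serve the mediator work, and the two nostrils may be eluted together.

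**Effect of the rule on detection.** All inputs are assumptions: per-strip detection 0.85 and correlation 0.5, in a beta-binomial model with a = 0.85, b = 0.15, a + b = 1.

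- One strip: 0.850.
- Both nostrils positive: 0.85 × 1.85/2 = 0.786.
- Either nostril: 1 − 0.15 × 1.15/2 = 0.914.
- Any of 3: 1 − 0.08625 × 2.15/3 = 0.938.
- Any of 6: 0.965.

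With independent strips, both nostrils gives 0.85² = 0.7225, either gives 1 − 0.15² = 0.9775, and any of 6 exceeds 0.999. With perfect correlation every rule gives 0.85. If the two nostrils form one eluate, the either/both contrast disappears and the ceiling is any of 3.

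**False positives.** At an assumed 2% per strip and correlation 0.5: 3.0% for either nostril and 4.8% for any of 6. If independent: 1 − 0.98² = 4.0% and 1 − 0.98⁶ = 11.4%.

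**Viral load with no true difference.** Expected maximum × an assumed strip SD of 0.5 log10: 0.564 × 0.5 = 0.28 for 2 strips and 1.267 × 0.5 = 0.63 for 6. This arises only if the highest strip is used.

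**Repeated days.** For an assumed 5 daily pairs and correlation 0.5, the design effect is 1 + 4 × 0.5 = 3 and √3 = 1.73. Intervals are too narrow by that factor only if clustering is ignored.

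**Yardstick.** The exact 95% interval for 28/30 is 77.9% to 99.2%, a width of 21.3 points; for 27/30 it is 73.5% to 97.9%, a width of 24.4. Under the central assumptions, moving from both nostrils to either nostril shifts detection by 91.4 − 78.6 = 12.8 points, inside the precision of one group. With independent strips the shift is 97.75 − 72.25 = 25.5 points, slightly outside it.

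**Reference.** Naming NPA as the reference would not remove its own error. Suppose SAM has true sensitivity 0.95 and specificity 0.98, and NPA has specificity 0.99 and sensitivity 0.80, at prevalence 0.7. Apparent SAM specificity is then (0.7 × 0.05 × 0.20 + 0.3 × 0.98 × 0.99)/(1 − 0.563) = 0.298/0.437 = 0.68. That is a matter of interpretation whichever rule is written down.

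**What the text leads an analyst to do.** The stated order puts an NPA after a nasal SAM. The closest sample in time, and the one with which the NPA forms a collection episode, is the SAM just before it. Other sessions that day are at least 4 to 6 hours away, and with three sessions the furthest can be 8 to 12 hours away. Pairing with the preceding SAM needs no new information.

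**The case for a change.** The strongest opposing case is that a pilot label excuses the absence of a power calculation but not of a defined primary comparison. The order and the 10-minute interval are collection rules: they do not say which daily session the NPA follows, which nostril enters the analysis, or what happens to later days. The direction of the any-positive effect needs no assumption, strip counts vary with the presence of tubes, and the result may shape how virus is sampled in the later study. One paragraph would close the gap without adding infants or samples.

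Most of the factual part stands. There is no analysis rule, and stating one would be tidy. The step to a necessary change does not follow. Any-of-6, highest-strip and unadjusted daily pairs are the extreme options, and the plan proposes none of them. A single strip, the first pair per infant and no pooling across groups would be one reasonable set among several; a repeated-measures model on all pairs is equally defensible. Writing down one set would not replace a worse stated method, because no method is stated. The reference question is also smaller than it looks: NPA is the method named in the comparison, and agreement against it is the same calculation as sensitivity and specificity with NPA as reference.

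**Conclusion.** No change to the plan is needed. The gap is genuine: sensitivity, specificity and quantitation are listed without an analysis rule, and strips outnumber NPAs in all four groups that have both, whenever both nostrils are used. It is a gap that competent analysts fill sensibly, by comparing each NPA with the SAM taken just before it, taking NPA as comparator, and allowing for repeated pairs within an infant.

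The size of any effect is not known from the documents. Under assumed inputs, detection could range from 79% (both nostrils) to 91% (either), and to 97% (0.965) with any of 6; the effect is zero if strips agree perfectly and larger if they are independent. The any-of-6 figure also requires every strip to be assayed separately, which the documents do not say. These figures illustrate sensitivity to a choice and do not show an error. The study is a pilot with 30 infants per group and no test, margin or decision rule for the method comparison, so its by-group results will be descriptive. The conclusion would differ if the plan stated an any-strip or highest-strip rule, or attached a formal decision to the comparison; it does neither.
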